 - c) greater improvement or lesser impairment of quality of life after reconstruction of floor of lesser pelvis
2. To study if the different rehabilitation programmes used reflect differences in outcome measures in subgroup analyzes for both methods of reconstruction
3. To compare the health economic costs with the two techniques and to perform a cost-utility analysis (QALYs gained). The health economic analysis is optional to participating centres. Costs and health economics will be calculated only in centres that have routine registration (in electronic databases) of operation time, time at ICU, days in hospital, connected reoperations, connected readmissions and outpatient visits related to the index operation.

Investigational plan

Endpoints of study

1. Primary endpoint: Performance in Timed-stands test (TST)[9, 10]reflecting physical performance at 6 months from operation.
2. Secondary endpoints:
 1. Change in physical performance (3 months, 6 months and 1 year compared to preoperative)
 2. Primary wound healing assessed with the Southampton Wound Assessment Scale (SWAS)[11] at 3 months from operation
 3. Complications according to classification by Dindo-Clavien[12] (3 months, 6 months and 1 year)
 4. Proportion of persistent perineal sinus or fistula (3 months, 6 months, 1 year)
 5. Ability to sit (3 months, 6 months, 1 year)
 6. Change of pain and discomfort in gluteal region measured with VAS (3 months, 6 months and 1 year compared to preoperative)
 7. Change of quality of life measured with EQ-5D and EORTC forms C30 and CR29 (3 months, 6 months and 1 year compared to preoperative)
 8. Quality of life spot measures at 3 months, 6 months and 1 year

9. Length of hospital stay, costs of surgical treatments and QALYs gained at one year
10. Local recurrence during study period

Hypotheses of study

Primary hypothesis:

1. The reconstruction of lesser pelvis floor with APCI will result in better physical performance in operated patients compared to patients operated on with GMF.

Secondary hypotheses:

1. The assumed decrease of physical performance after the APCI operation will be less than after the GMF operation.
2. The reconstruction of lesser pelvis floor with APCI will result in better wound healing and less wound complications than the GMF operation.
3. The reconstruction of lesser pelvis floor with APCI will result in better ability to sit and lesser pain and discomfort in the gluteal region than the GMF operation,

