- Inform physiotherapist and book the visit
- Include patient information of NEAPE study with invitation to patient
- Include preoperative quality of life forms
- Include information of routine registration in study register and CRC register

Enrol

Surgeon

Preoperative visit to attending surgeon

- Check for eligibility
- Inform patient of NEAPE study
- Get informed consent if conditions met and file the document
- Randomise/Enrol if decision of standard EAPE can be made

Physiotherapist or study nurse

Preoperative visit to physiotherapist (before RT if possible)

- Fill preoperative form (P1)
- Check and collect QoL forms and inform patient if necessary for complete data
- Perform physical tests and register results on form (P2)
- Register all collected data into the electronic database on Internet

Surgeon

Operation

- Check for eligibility
- Operate according to allocation and NEAPE study standard
- Randomise/Enrol if decision of standard EAPE can be made only at this point
- Follow NEAPE perioperative standards

Study nurse Weekly check-up that all patients operated on with APE or EAPE at the hospital are either randomised or registered and that correct/completed registration data is saved

- This will be the final data for non-randomised patients

Follow-up

Study nurse Send invitation for postoperative visit at 30 days

- Include postoperative quality of life forms

Surgeon

30 days postoperative NEAPE follow-up visit to attending surgeon

- Fill form of staging and TNM classification (form S1)
- Check for early complications and register on form (S2)
- Classify wound healing and all complications on form (S3)

Study nurse Send invitation for postoperative visit at 3 months

- Include postoperative quality of life forms

Surgeon

3 months postoperative NEAPE follow-up visit to attending surgeon

- Check for late complications and register on form (S4)
- Classify wound healing and all complications on form (S3)

Physiotherapist or study nurse

3 months postoperative NEAPE follow-up visit to physiotherapist

- Check and collect QoL forms and inform patient if necessary for complete data
- Perform physical tests and register results on form (P2)
- Fill postoperative form (P3)
- Register all collected data into the electronic database on Internet

Study nurse Send invitation for postoperative visit at 6 months

- Include postoperative quality of life forms

Surgeon

6 months postoperative NEAPE follow-up visit to attending surgeon

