Blinding in surgical studies is hard to accomplish. This study is performed without attempts for blinding and thus the attending surgeon, the examiner of physical performance and the patient do not have to be blinded.

Concomitant therapy

Pre- and postoperative radiotherapy or chemo radiotherapy can be utilised according to multidisciplinary team decisions at each centre.

Postoperative rehabilitation programmes

Due to already existing routines, we consider it not realistic to prescribe only one uniform programme. Instead, the patients will be allocated to either an established programme[7] or to an accelerated programme that has been used in another centre. Both rehabilitation programmes are standardized, written and should be followed explicitly. The descriptions of both programmes can be downloaded from the study webpage at www.norrlandskirurgi.se.

Participating centres must choose one of the rehabilitation programmes and use that program for all their study patients. The rehabilitation programmes at hand are studied earlier and considered safe [21].

Evaluation of outcome measures and safety

Measures of physical performance

The study physiotherapist or nurse will examine measures of physical performance.

A "timed-stands test" is to be performed by recording the time needed to stand ten times from a standard chair[9, 10]. The test gives a measure of lower extremity muscle strength, muscle coordination and tenderness of the gluteal region (caution when sitting) and gives the possibility to correlate the results to a reference population studied earlier[9]. The test is validated.

A complementary step test is performed at some participating centres (optional test)[22].

The study physiotherapist or nurse will process measures of quality of life, pain, discomfort and ability to sit. Data will be registered on forms (see Appendix) or directly in the electronic database.

Quality of life is measured with the global instrument EQ-5D and the cancer specific instrument EORTC QLQ-C30 and QLQ-CR29. The forms will be sent to the patient prior to the follow-up visits and the study physiotherapist or nurse who cares for the data to be registered in the study database will collect the completed forms. Completeness of data should be checked during the visit so that any incomplete data can be corrected together with the patient.

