Pain in different postures will be evaluated with a 100 mm visual analogue scale (VAS). Discomfort and anatomical distribution of pain will be mapped with a specific figure or chart where patients can indicate areas of discomfort or pain.

The patients' ability to sit will be evaluated during the initial interview by observation of how the patients sit in the chair during the first 10 minutes. The patients will not be told about the observation made by the examiner. Three categories of ability to sit will be used, a) normal sitting during 10 minutes, b) sitting with some kind of aid (cushion or ring) or compensating weight bearing with a not relaxed posture and c) not able to sit at all.

Optional tests for skin sensitivity in the perineal area (with von Freys filament) and pressure threshold for pain (with Algometer) at the sciatic tubercles will be measured at some centres.

Measures of complications including the surgical and oncologic result

Measures of complications and the surgical as well as the oncologic result will be considered and registered **by the attending surgeon** during the follow-up visits. Postoperative complications will be classified according to Dindo-Clavien[12] and registered on a paper form (see Appendix) alternatively directly in the electronic database via the web application.

Definitions of surgical result and wound healing measures

The local surgical result in the perineal wound will be classified according to the Southampton Wound Assessment Scale[11] that is validated[23].

- 0 Normal healing
- I Normal healing with mild bruising or haematoma
- II Erythema plus other signs of inflammation
- III Clear or haemoserous discharge
- IV Pus
- V Deep or severe wound infection with or without tissue breakdown; haematoma requiring aspiration

The grade of the above wound healing classes is registered for each patient at the 3 month follow-up event and applies for the present status or for the postoperative period up to 3 months. The worst class noted during the follow-up should be recorded.

In addition, at all follow-up visits

- a) persisting sinus of fistula in perineal wound and

- b) removal of implant (only APCI) and
- c) excision of a myocutaneous flap in part or whole (only GMF) and
- d) occurrence of perineal hernia should be noted.

The healing of the laparotomy wound is not graded in this study but disturbances of laparotomy wound healing will be registered as an adverse event among other circumstances, see below.

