Appendix

Form S1: Surgeon, first postoperative visit, workup and TNM

(same as Swedish CRC register at www.incanet.se, paper form or www.norrlandskirurgi.se outside Sweden)

SEPARATE DOWNLOAD

Form S2: Surgeon, early complications within 30 d

(same as Swedish CRC register at www.incanet.se, paper form or www.norrlandskirurgi.se outside Sweden)

SEPARATE DOWNLOAD

Form S3: Surgeon, all postoperative visits

SEPARATE DOWNLOAD

Form S4: Surgeon, late complications, postoperative visits later than 30 days

(same as Swedish CRC register at www.incanet.se, paper form or www.norrlandskirurgi.se outside Sweden)

SEPARATE DOWNLOAD

Form P1: Physiotherapist, pre-treatment

Inskrivningsformulär (ifylls av sjukgymnast/ studiesjuksköterska)

SEPARATE DOWNLOAD

Form P2: Physiotherapist, test form

NEAPE Bedömningsformulär för fysisk funktion

(sjukgymnast/studiesköterska)

preoperativt 3 mån 6 mån 12 månader

SEPARATE DOWNLOAD

Form P3: Physiotherapist or study nurse, postoperative

NEAPE uppgifter om RT och OP

Fylls i senast 3 månader efter operation.

SEPARATE DOWNLOAD

QoL formulär EQ-5D och EORTC C30 och CR29 på följande sidor

SEPARATE DOWNLOAD

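### The examiner who times the effort-dependent primary test is excused from blinding for a reason that fits the surgeon, and may also complete the operation form before that test; withholding the allocation where staffing permits would reduce the risk of bias.

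*Protocol*

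**What the plan says.** The Blinding section opens with a general reason, "Blinding in surgical studies is hard to accomplish", and concludes that, along with the attending surgeon, "the examiner of physical performance and the patient do not have to be blinded". It gives no reason specific to the examiner.

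The primary endpoint is "Performance in Timed-stands test (TST)[9, 10]reflecting physical performance at 6 months from operation" (Endpoints of study). Under Measures of physical performance, the study physiotherapist or nurse runs the test by "recording the time needed to stand ten times from a standard chair". The same section says that the result reflects strength, coordination and tenderness, including caution when sitting. The physiotherapist or nurse is also responsible for the ability-to-sit outcome, which is placed in one of three categories "by observation of how the patients sit in the chair during the first 10 minutes".

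In the flowchart, the 3-month block for the physiotherapist or study nurse lists both the physical tests (form P2) and form P3. The Appendix names the latter "Form P3: Physiotherapist or study nurse, postoperative", heads it in Swedish as data on radiotherapy and operation, and requires it by 3 months after surgery. The form is a separate download, so its fields are not visible.

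The Summary of study design promises a separate detailed examination protocol and a pre-study standardisation meeting. Nothing in the protocol limits what the examiner knows about the allocation.

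**The concern.** Whether blinding is feasible has to be asked person by person. The surgeon cannot be blinded, and the patient hardly can be. The examiner takes no part in the operation, and the test is rising from a chair, for which the protocol requires no view of the wound. Wound grading belongs to the surgeon.

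The TST is a stopwatch measurement, but it depends on effort. Encouragement, and the judgement of when the test starts and ends, can shift with what the examiner expects. The middle sitting category includes a posture that is not relaxed, which is a judgement. The expectation is written into the protocol: the Introduction stresses the role of the gluteus maximus in hip extension, posture and balance, the primary hypothesis favours the implant (APCI), and the sample size assumes low performance in 63% with the flap (GMF) against 30% with the implant. An expectation effect would therefore tend to favour the trial's hypothesis. It would also help a noninferiority claim for the implant. Bias that enters at measurement cannot be removed reliably in the analysis.

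**Working it through.** **1. Is the examiner kept from knowing the arm?** Three places bear on this.
- Blinding section: the examiner is expressly excused.
- Flowchart and Appendix: the person who does the testing may also complete P3. P3 is due by 3 months and the primary test is at 6 months, so any operation details on it would be known first.
- Summary of study design: a manual and a meeting standardise how the test is done. They do not conceal the allocation.

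**2. Could existing roles separate the tasks?** The flowchart already distinguishes surgeon, study nurse (invitations, registration checks) and physiotherapist or study nurse (testing). P3 can therefore go to someone who does not test. However, a centre qualifies with resources for examination by a physiotherapist or a nurse, so in some centres one person may do everything.

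**3. The protocol's sample size, as the basis for the number evaluable.** Inputs from the Sample size section: 63% against 30%, alpha 0.05 (two-sided assumed), power 90%, 20% loss.

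n = (p1q1 + p2q2)(z_α + z_β)² / (p1 − p2)²
= (0.2331 + 0.2100)(1.960 + 1.282)² / 0.33² = 42.8, so 43 evaluable per arm.

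43 / 0.8 = 53.75, so 54 per arm and 108 in total, as stated. At 80% power the formula gives 32 evaluable, 40 per arm and 80 in total, also as stated. Masking the examiner does not change these numbers.

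**4. Illustration in seconds.** The protocol gives neither an SD for the TST nor an examiner effect. Assume an SD of 8 s (range 6 to 10), a systematic examiner effect b of 1 or 2 s between arms, no true difference, and 43 evaluable per arm.

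d = b / (SD·√(2/43)); rejection probability = Φ(−1.96 + d) + Φ(−1.96 − d)

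| b | SD 6 s | SD 8 s | SD 10 s |
|---|---|---|---|
| 1 s | 12% | 8.9% | 7.5% |
| 2 s | 34% | 21% | 15% |

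For b = 2 s and SD 8 s: standard error 8 × 0.2157 = 1.725, d = 1.159, and 0.212 + 0.001 = 0.21.

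**5. Illustration on the proportion scale.** The trial is powered on the proportion with low performance, and the Primary analysis section allows that proportion as the comparison. Assume 63% in both arms and 54 × 0.8 = 43.2 evaluable per arm. If biased assessment lowers the observed implant rate by an assumed 5 or 10 points, the chance of a false finding in favour of the implant rises from 2.5% to 6.9% or 15.3% (pooled two-proportion z test). The message is the same: a modest systematic effect matters at this sample size.

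**The case against.** The open design is disclosed and a reason is given, so this is a design choice and not an error or contradiction. The TST is a timed measurement that the protocol calls validated, and the unseen manual may well cover encouragement and start and stop rules. All of this stands and keeps the point moderate, but standardising a test is not the same as concealing the arm.

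A reader might infer that the plan itself unblinds the examiner through P3. The documents do not support that. P3 may be completed by a physiotherapist or a study nurse, so a nurse who does not test could already do it. That P3 names the reconstruction is inferred only from its heading.

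P3 is also not the only route of disclosure. The physiotherapist or nurse checks quality-of-life forms, handles pain data and the pain chart, and reports serious adverse events, and the unblinded patient sits in interview with the examiner. Moving P3 alone would achieve little, so the order of tasks matters as well.

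A reader might also take 9% to 21% as the trial's expected false-positive rate. It is not: the SD and the effect are assumed, and the calculation attributes the whole effect to the examiner. Bias from the patient's own effort would remain after the change, so the figures do not measure what the change would gain.

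**Conclusion.** The point holds as a proportionate design improvement. The protocol waives blinding for the one assessor of the primary endpoint who could plausibly be kept unaware of the arm, for a reason that does not fit that role, and it permits that person to complete operation data before the primary test. The likely direction is towards the trial's hypothesis; the size is unknown. The illustrative rise from 5% to about 9% (1 s) or 21% (2 s) rests on an assumed SD of 8 s, 43 evaluable per arm and no true difference. Across SDs of 6 to 10 s the range is about 7.5% to 34%. The stated sample size reproduces and is unaffected.

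**What to change.** Reword the Blinding section to say that the surgeon and the patient are not blinded, but that, wherever existing staffing permits, the examiner for the TST and the sitting observation is not told the allocation. In addition:

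- Assign P3 to the surgeon or to a study nurse who does not do the testing.
- Ask patients not to tell the examiner which operation they had.
- At each visit, do the sitting observation and the TST, with the patient clothed, before the pain chart, the quality-of-life check and any optional perineal sensitivity test.
- Add an item to P2 on whether the arm became known to the examiner, and report it descriptively by arm. Do not split the primary analysis by it: poor sitting or gluteal pain may itself reveal the arm, so such a split would condition on a post-randomisation variable.

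The cost is protocol and form wording and some reassignment of tasks among existing staff, with no extra patients or visits. The downside is that masking will be partial, especially in centres with a single examiner, and that effort bias from the unblinded patient remains.

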4. The reconstruction of lesser pelvis floor with APCI will result in better quality of life than the GMF operation.
5. The reconstruction of lesser pelvis floor with APCI will result in lower costs of treatment and more QALYs gained than the GMF operation.
6. The local recurrence rate is not related to the method of reconstruction of lesser pelvis

Noninferiority hypothesis:

1. The reconstruction of lesser pelvis floor with APCI will result in clinically equivalent physical performance provided that results will be within defined noninferiority margins, see below.

Noninferiority margin:

The noninferiority margin is set to 10%. Interpretation, see section Data analysis methods.

Summary of study design

The study is multi-centre, prospective randomised and with parallel assignment. Centres that treat locally advanced rectal cancers with the extended abdominoperineal excision of rectum (EAPE)[7] can participate provided that:

1. the operative technique is standardized according to this protocol, see section Surgical methods
2. the centre/unit has resources for examinations of participants by a physiotherapist or a nurse
3. the centre/unit has one investigator in charge of the study locally
4. the centre/unit has an operative volume that enables at least 6 patients to be included/randomised during the anticipated three year study phase for inclusions

Centres that do not operate the rectal cancers included in this study can participate by arranging the preoperative examination and physical tests as well as follow-up of patients that are referred to other centres for the operation. In these cases the operating centre cares for the randomisation, operation and start of postoperative rehabilitation while the study follow-up and final rehabilitation can be completed at the patients' primary referral

hospital. The primary referral hospital needs a site investigator in charge of study patients just like centres that do the operations.

Patients with primary or recurrent cancers of rectal origin can be included but individual patients can be included only once. Concomitant therapies are allowed and preoperative or postoperative radiation therapy and/or chemotherapy may be given or not according to local multidisciplinary team (MDT) decisions.

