Once per year an independent advisor that together with the PI has the authority to stop the study if serious unexpected safety issues can be observed will evaluate the collected data of clinical adverse events. If the independent advisor and the PI make a decision to stop the study, the decision must be written and motivated in detail and distributed to all participating centres without delay.

Quality control and quality assurance

To ensure accurate and reliable data the study administration will do the following:

- Provide instructional material to the study sites, as appropriate (manual for physical examination etc.)
- Update study homepage at www.norrandskirurgi.se with relevant information and study material
- Start-up training, meeting with investigators
- Be available for consultation
- Conduct quality review of database (a monitor may be sent to participating centres)

Data analysis methods

Sample size

The sample size is calculated with the following assumptions:

- Estimated proportion of patients with low performance in TST with GMF 63%
- Estimated proportion of patients with low performance in TST with APCI 30%
- Estimated loss of data/cases 20% (mortality etc.)

The calculation gives that a total of 108 patients (54 patients in each study arm) are needed with 90% power and a significance level of 0.05 (alpha).

If the anticipated three-year inclusion phase of the study is too short for including 108 patients an alternative power calculation with 80% power will be used instead and the study will include a total of 80 patients only before the inclusion phase will be closed.

Interpretation of noninferiority

The noninferiority margin for the study is set on the basis of a minimally important clinical effect, which is a subjective judgement of the best expertise available. This approach remains the only alternative since there are no historical placebo controlled trials in the field for guidance and for practical reasons such trials are not possible to conduct.

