We consider that a minimally important clinical effect applies for this study if results differ less than 10%. The noninferiority margin is thus set to 10%. This means that the results from study arms are considered clinically having no important differences if the results from test operation (APCI) differ less than 10% in the main outcome. We claim noninferiority for test operation if the result will be in the range less than 10% inferior result up to a trend for superior result but not statistically significant for the main outcome. If the result shows a statistically significant difference we claim superiority (or inferiority) of the test operation. If we find noninferiority based on the main outcome we may still draw conclusions about which operation should be preferred, based on results from secondary outcomes.

Data to be analyzed

All primary analyses in this study will be performed according to the intent-to-treat (ITT) principle, that is, patients will be allocated to treatment groups corresponding to their assigned treatment, even if the patient does not receive the correct treatment.

The intention-to-treat population will consist of all randomised patients who are operated with EAPE.

Per-protocol analyses are secondary and may be used if special circumstances motivate to use such. If noninferiority is to be stated we will do a per-protocol analysis in addition to the ITT analysis and if both analyses are non significant it will give more evidence of noninferiority. The per-protocol population will consist of all patients in the intent-to-treat population who have met all protocol requirements and who have successfully completed the trial up till one year.

Patient disposition

Reasons for discontinuations in the study will be compared between the 2 treatment groups. Result tables or the Consort[24] diagram will reveal the number and proportion of patients who have completed the study as well as patients that have discontinued, grouped by reason for discontinuation.

Patient characteristics

Age, gender, primary or recurrent rectal cancer will be registered when the patient is randomised via the web application and will be included in the summary reports.

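### Noninferiority is claimed when the observed deficit is under 10% and the test is non-significant; no confidence limit is compared with the margin, so the claim has no error control

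*Protocol*

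**What the plan says.** The Primary objective of the protocol names two possible conclusions for APCI, superiority or noninferiority. The Noninferiority margin section gives 10% without saying of what.

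Interpretation of noninferiority gives the decision rule: "We claim noninferiority for test operation if the result will be in the range less than 10% inferior result up to a trend". The range ends at a favourable trend that falls short of significance. Significant results are handled separately: "If the result shows a statistically significant difference we claim superiority (or inferiority) of the test operation".

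Data to be analyzed adds a per-protocol analysis whenever noninferiority is to be stated, and says of the two analyses: "if both analyses are non significant it will give more evidence of noninferiority".

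Sample size rests on a superiority comparison of the proportion with low timed-stands performance, 63% with GMF against 30% with APCI. Primary analysis compares the test in seconds and only allows the proportion beyond the reference limit as a possible parameter.

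**The concern.** A noninferiority claim needs the data to exclude a deficit as large as the margin. This rule asks for two other things: an observed deficit below 10%, and a non-significant difference test. The first ignores sampling error. The second is met most easily when the data are uninformative, and it says nothing about the margin. Repeating it in the per-protocol set does not turn it into evidence.

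Two smaller faults sit in the same rule. The 10% could mean 10% of the time in seconds or 10 percentage points of low performers, and the protocol uses both scales. A deficit of 10% or more that is not significant has no named conclusion.

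At stake is one of the two conclusions the trial was set up to reach, and the one that applies whenever superiority is not shown.

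**Working it through.** **The plan's own sample size.** Inputs from Sample size: 63% and 30%, 20% loss, alpha 0.05 (taken as two-sided), 90% power, with a fallback at 80%.

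- 90%: n = (1.960 + 1.282)² × (0.63×0.37 + 0.30×0.70) / 0.33² = 10.507 × 0.4431 / 0.1089 = 42.75, so 43 evaluable per arm. 43/0.8 = 53.75, so 54 per arm and 108 in total, as stated.
- 80%: 7.849 × 0.4431 / 0.1089 = 31.94, so 32 per arm. 32/0.8 = 40, so 80 in total, as stated.

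**The rule on the proportion scale.** Let the numbers of low performers be binomial, with rate p under GMF and p + d under APCI. Noninferiority is claimed if the observed APCI-minus-GMF difference is below 0.10 and the pooled z-test has |z| < 1.96. Exact probabilities were summed over all outcome pairs for p = 0.30, 0.50 and 0.63. The first and last are the plan's rates; 0.50 is an assumed value between them.

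| True deficit d | Claimed, 43 per arm | Claimed, 32 per arm |
|---|---|---|
| 0 | 0.81-0.83 | 0.78-0.81 |
| 10 points | 0.51-0.52 | 0.53 |
| 15 points | 0.32-0.33 | 0.36-0.37 |
| 20 points | 0.15-0.18 | 0.20-0.22 |

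With no losses at all, the figure at 10 points is 0.51 at 54 per arm. At 40 per arm it is 0.45, because a difference of exactly 10 points is attainable there and does not count (0.54 if it does).

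Requiring instead that the upper 95% Wald limit lie below 10 points gives 0.025-0.028 at a true 10-point deficit.

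The non-significance condition protects little. At 43 per arm and a true 10-point deficit, the test is non-significant 83-85% of the time.

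**Precision.** The 95% half-width is 1.96 × √(2p(1−p)/n). At n = 43 it is 1.96 × 0.0988 = 0.194 for p = 0.30 and 1.96 × 0.1041 = 0.204 for p = 0.63. An observed deficit just under 10 points is therefore compatible with a true deficit of nearly 30.

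**Unnamed zone.** At 43 per arm and a true 10-point deficit, a non-significant observed deficit of 10 points or more occurs with probability 0.31-0.33.

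**The rule on the seconds scale.** The protocol gives no SD. Assume a margin of 10% of the mean time, equal coefficient of variation (CV) in both arms, approximate normality and 43 per arm. Then SE = CV × √(2/43), and noninferiority is claimed if the estimate lies between −1.96 SE and the smaller of 0.10 and 1.96 SE. At a true deficit of 10%:

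- CV 0.15: SE 0.0323, cut-off 0.0634, Φ((0.0634 − 0.10)/0.0323) = Φ(−1.13) = 0.13.
- CV 0.20: SE 0.0431, cut-off 0.0845, Φ(−0.36) = 0.36.
- CV 0.25: SE 0.0539; 1.96 SE = 0.106 exceeds 0.10, so the cut-off is 0.10 and the probability is about 0.50. It stays near 0.50 for larger CVs.

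At lower variability the rate drops (0.004 at CV 0.10), because a margin-sized deficit then tends to be significant and is called inferiority. The error rate is set by the unknown spread of the data, not by the rule.

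**The case against.** The primary hypothesis and the sample size are for superiority, and this rule leaves that test alone. If the truth is near 63% against 30%, the noninferiority branch will rarely be reached. That is fair, but the protocol names noninferiority in its primary objective, and the branch matters exactly when the planning assumption fails.

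It could also be said that the details belong in a statistical analysis plan. The protocol, however, does not leave the rule open: it states one, and that rule is wrong.

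A reader might infer three stronger things that the documents do not support:

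- *That a small or noisy trial would endorse the implant by default.* The 10% cap on the observed deficit prevents this. With equal arms the chance of a claim falls from 0.81-0.83 at 43 per arm to 0.78-0.81 at 32. At a 10-point deficit it hardly moves (0.51-0.52 to 0.53). The 80-patient fallback adds little to the problem.
- *That the rule has no inconclusive outcome.* A non-significant deficit of 10% or more earns neither claim. The zone exists but is not named.
- *That the false-claim rate is about one half whatever the scale.* This holds on the proportion scale. On seconds it depends on a CV that the protocol does not give.

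**Conclusion.** The rule is wrong as written. It sets an observed result against the margin, reads non-significance as support, and fixes no error rate for the noninferiority claim.

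On the proportion scale, and for GMF rates from 30% to 63%, the chance of a false claim at the margin is 0.51-0.52 with 43 evaluable per arm and 0.53 with 32, roughly twenty times the 0.025 of a confidence interval rule. On seconds it is about 0.13 to 0.50 for an assumed CV of 0.15 to 0.25 or more, with a relative 10% margin and 43 per arm. The missing scale for the 10% and the unnamed zone are lesser faults of the same rule. The superiority test and the sample size calculation are not affected.

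**What to change.** Replace the rule in Interpretation of noninferiority, and the matching sentence in Data to be analyzed, as follows:

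1. Name the single primary measure and state the margin on its scale.
2. Claim noninferiority only if the limit of the two-sided 95% confidence interval for APCI versus GMF on the unfavourable side lies inside the margin in both the intention-to-treat and the per-protocol analysis.
3. Claim superiority or inferiority if the intention-to-treat 95% interval excludes no difference in that direction, as the protocol does now. Say that inferiority takes precedence if a narrow interval lies wholly on the worse side but inside the margin.
4. Call every other result inconclusive.
5. Delete both criteria that rest on a non-significant test.
6. State that the sample size was set for superiority only, and give the expected half-width: about 19-20 points at 43 per arm on the proportion scale, for rates of 30% and 63%.

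The edit is to wording and adds no patients, but it has a real cost. On the proportion scale with truly equal arms, noninferiority would be shown only about 16-17% of the time at 43 per arm and 13-14% at 32. For 80% power with a 10-point margin, n = (1.960 + 0.842)² × 2p(1−p)/0.10², which is 330 evaluable per arm at p = 0.30, 393 at 0.50 and 366 at 0.63. After 20% loss that is 826 to 984 patients in total, against 108 planned. The protocol should therefore describe the noninferiority objective as having low power, and the sponsor should decide whether to keep it on those terms.
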